5.2 Intervention Risk

There is the potential risk of an interventional failure for study participants. The study results may not support the primary hypothesis that in patients with severely calcified femoral arteries, a pre-treatment with Shockwave intravascular lithotripsy intervention will not result in a decrease in femoral artery access site complications. It is possible that the intervention will prove to be less effective than the current standard method in which Shockwave intravascular lithotripsy is not used prior to access and placement of the TAVR delivery system.

Indications for Use—The Shockwave Medical Intravascular Lithotripsy (IVL) System is intended for lithotripsy-enhanced balloon dilatation of lesions, including calcified lesions, in the peripheral vasculature, including the iliac, femoral, ilio-femoral, popliteal, infra-popliteal, and renal arteries. Not for use in the coronary or cerebral vasculature.

Contraindications—Do not use if unable to pass 0.014" (M5, M5+, S4) or 0.018" (L6) guidewire across the lesion-Not intended for treatment of in-stent restenosis or in coronary, carotid, or cerebrovascular arteries.

Adverse effects—Possible adverse effects consistent with standard angioplasty include:

- Access site complications
- Allergy to contrast or blood thinner
- Arterial bypass surgery

- Bleeding complications
- Death
- Fracture of guidewire or device
- Hypertension/Hypotension
- Infection/sepsis
- Placement of a stent
- renal failure
- Shock/pulmonary edema
- target vessel stenosis or occlusion
- Vascular complications
- Risks unique to the device: device malfunction or failure
- Excess heat at target site.
- Allergic/immunologic reaction to the catheter material(s) or coating-Device malfunction failure, or balloon loss of pressure leading to device embolism, dissection, serious injury or surgical intervention
- Atrial or ventricular extrasystole-Atrial or ventricular capture

5.3 Psychological Risks:

A potential psychological risk could occur if patients feel a sense of coercion to participate in the trial. The likelihood is small because patients will be assured in the informed consent document and face-to-face discussion that participation is purely voluntary and they can withdraw their participation at any time. Other potential psychological or emotional risks of fear, anxiety, guilt, confusion, depression, or social stigma could occur, however this likelihood is small as we will provide as much information as possible during the consent and debriefing process.

5.4 Research Risk

Identifiable patient information will be securely stored by the study team. For this specific project, all information related to patients will be identified only by patient initials and study number. However, for research purposes, it may be required to collect PHI such as age, DOB, Medical Record Number and dates of diagnoses. Only the study team will have access to this data and it will not be shared with anyone outside of the study team. The greatest research risk, although rare, is the loss of confidentiality caused by unauthorized release or misuse of information from research records.

6. BENEFITS

Although there may be immediate clinical benefits for some patients in this trial who are assigned to the study intervention, the anticipated primary benefit is the future potential to decrease any vascular access complications that would lead to additional procedures or interventions, improve the safety of inserting the TAVR device delivery system.

Information obtained from this research may help patients in future achieve better health outcomes and provide clinicians with pertinent information about treating severely calcified femoral arteries prior to placement of the TAVR delivery system in attempts to make the

procedure safer for these particular patients. The treatment may be more effective than the treatments that are currently available.

7. ENDPOINTS/OUTCOMES

7.1 Efficacy

1. Evaluate for contrast extravasation post closure of femoral artery at the end of the procedure
2. Determine need for Vascular surgery consultation
3. If vascular complication, was PTA, stenting, or open surgery used
4. Number of perclose devices used to close the femoral artery access site
5. Determine presence of other vascular complications i.e. bleeding, hematoma, emboli etc.
6. Review lab values and vital signs to determine if there is any clinical deterioration (drop in hemoglobin, worsening of creatinine, development of hypotension/shock, infections/sepsis)
7. Determine if there is a difference between hospital length of stay
8. Assess for difference in pain/numbness in distal extremities post-procedure
9. Assess for differences in mortality related to complications between the groups
10. Failure of treatment

7.2 Safety

1. Number of related AE(s)
2. Number of related SAE(S)
3. Side effects reported by subjects or observed by study team

8. ADVERSE EVENTS AND SERIOUS ADVERSE EVENTS

AEs that are considered possibly, probably or definitely related to the study procedure will be recorded in the CRFs. AEs will be assessed starting with onset, and evaluation will continue until resolution is noted, or until the investigator determines that the patient's condition is stable.

All AEs will be characterized by the following:

- AE name
- Start and Stop dates
- Relationship to study procedure
- Severity
- Action taken
- Outcome

Relationship

The investigators will assess the AEs and using their clinical judgment will assign an attribution to the AE using the following categories:

- **Unrelated** – The AE is clearly NOT related to the study procedure
- **Unlikely** – The AE is doubtfully related to the intervention

- **Possibly** – The AE *may be related* to the study procedure
- **Probably** – The AE *is likely related* to the study procedure
- **Definitely** – The AE *is clearly related* to the study procedure

Severity

The severity of the AEs should be graded by the investigator as follows:

- **Mild** – Transient discomfort; no prescribed medical intervention/therapy required and does not interfere with daily activities.
- **Moderate** – Low level of discomfort or concern with mild to moderate limitation in daily activities; some assistance may be needed; medical intervention/therapy required.
- **Severe** – Discomfort and limitation in daily activities, assistance required; medical intervention/therapy required.

Action Taken

The action taken in response to the AE should be reported using the following categories:

- None
- Procedure or physical therapy
- Withdrawn from study due to AE
- Hospitalization
- Prescription drug therapy
- Non-prescription drug therapy
- Other (specify)

Outcome

The clinical outcome of an AE should be characterized as follows:

- Resolved without sequelae
- Resolved with sequelae (specify)
- Ongoing (i.e. continuing at time of study discontinuation)
- Death
- Unknown/lost to follow-up
- Other

SAE Reporting

All SAEs will be documented in the CRFs. SAEs will be reported to the local IRB per the following guidelines:

Adverse event reports will only be submitted to the local IRB if they are determined by the principal investigator to be: unanticipated, serious, and possibly, probably or definitely related to a research study procedure.

An SAE determined to be due to worsening of a pre-existing co-morbidity unrelated to the procedure will not be documented as an SAE. Such as a repeat hospitalization due to worsening COPD, diabetes, etc. As these can be expected and unrelated to the study in patients with these pre-existing conditions.

SAEs meeting these criteria (except for deaths) must be reported to the IRB *within 5 working days* of the study team's notification of occurrence. Deaths that are unanticipated and are possibly, probably or definitely related to a research study procedure must be reported to the IRB *within 24 hours* of notification of occurrence. Any relevant follow-up information regarding the SAE should be submitted to the IRB as soon as it becomes available and/or upon request. SAE reports to the IRB must include the following: subject identifier, adverse event or problem description, the event relationship to the test article or underlying condition, seriousness assessment, whether the event was anticipated or unanticipated, type of report (initial or follow-up), date of injury, whether the intervention was stopped, and, if so, whether it was re-started, and whether the event provides new risk information that alters the risk-benefit assessment and/or should be added to the informed consent disclosure.

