3.3 Study Duration

We plan to enroll up to a total of 100 patients, 50 patients in each group. The total study duration will be approximately 12 months post IRB approval and study initiation. We will follow patients for 3 months post procedure for any adverse events; however, we would expect to see them within 3 days if there are events to occur.

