4.3.3 Study Intervention Administration

The patient will be randomized using a randomized generator to either Group 1 (intervention) or Group 2 (control).

Study approach will be administered by [name].

1. We will first obtain access on the Common Femoral Artery (CFA) contralateral to the planned large bore access.
2. We will use a 6 F sheath and an Omnipulse or similar catheter over an 0.035 Benson, Wholey or Advantage- glide wire.
3. We will then advance a 0.014 wire distal into the external iliac and remove the Omnipulse catheter.
4. Over the 0.014 wire, we will advance Shockwave 60 mm balloon sized to the distal CFA balloon and perform IVL of the contralateral CFA.
5. After completing shockwave IVL we will then access the CFA with Fluoroscopy/US guidance and preclose followed by placement of a large bore sheath.

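### Section 8 enters non-serious AEs in the CRF only if judged related to an undefined study procedure, and leaves co-morbidity SAEs unclear, so the safety record cannot be compared by arm without relying on attribution

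*Combined protocol and SAP*

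**What the plan says.** Section 8 of the protocol sets the recording rule for adverse events: "AEs that are considered possibly, probably or definitely related to the study procedure will be recorded in the CRFs". It then says "All AEs will be characterized by the following" and lists relationship among the characteristics. The investigators assign relationship by clinical judgment on a five-level scale: unrelated, unlikely, possibly, probably, definitely. Four of the five levels are defined by reference to the study procedure. The unlikely level reads "The AE is doubtfully related to the intervention".

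Serious events have a separate rule with no relatedness condition: "All SAEs will be documented in the CRFs". Later in the same section comes an exception: "An SAE determined to be due to worsening of a pre-existing co-morbidity unrelated to the procedure will not be documented as an SAE". The example given is "Such as a repeat hospitalization due to worsening COPD, diabetes, etc".

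Section 3.3 says "We will follow patients for 3 months post procedure for any adverse events". Section 7.2 lists three safety endpoints: the number of related AEs, the number of related SAEs, and side effects reported or observed. Only the third carries no relatedness condition.

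**The concern.** In a comparative trial, a safety record should let a reader set all events in one arm against all events in the other and treat causal attribution as a separate, checkable judgment. Here attribution comes first and decides whether a non-serious event is entered at all. The people making the judgment are the investigators, and the plan describes neither masking nor independent review. Section 4.3.3 writes out only the lithotripsy sequence, so it is not clear what a control patient's event should be judged against.

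At stake is whether a difference, or a lack of difference, in related events between the arms can be interpreted. If unrelated events are not in the database, nobody can later tell whether the arms differed in what happened or in how it was attributed. The co-morbidity exception raises the same difficulty for a class of serious events, namely readmissions for pre-existing disease.

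**Working it through.** No figure in the plan bears on this point. The sample size in Section 9.1 concerns complications, not adverse event counts. The check is therefore a comparison of texts.

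**Step 1: what reaches the CRF under Section 8 as written.**

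| Event | Entered in the CRF? |
|---|---|
| Non-serious, judged possibly, probably or definitely related | Yes |
| Non-serious, judged unlikely or unrelated | Not provided for |
| Serious, outside the co-morbidity exception | Yes, whatever the relationship |
| Serious, co-morbidity worsening judged unrelated | Not as an SAE; otherwise not stated |

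The AE rule names 3 of the 5 levels, leaving 5 − 3 = 2 outside it. The word *only* does not appear. But naming three levels would serve no purpose if all five were entered, and the SAE rule in the same section is written without any such condition. In the last row, if such an event were treated as an ordinary AE it would be unrelated by definition and so fall outside the AE rule as well.

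**Step 2: what relatedness is judged against.** *Study procedure* is never defined. Two readings are open:

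- *Lithotripsy only.* Section 4.3.3 labels Group 1 alone as intervention and sets out only the lithotripsy steps. One line of the scale refers to the intervention.
- *The access procedure in either arm.* Sections 3.4.1 and 3.4.2 require every candidate to understand study procedures before randomization. Section 11.2 has investigators monitor reactions to study procedures with no limit by arm. Section 5.1 links the intervention to guided access and the modified Seldinger technique, which Section 3.1 gives to both arms.

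The choice can matter. Section 5.1 lists allergic or immunologic reaction among the risks of TAVR itself, and Section 5.2 lists it as a possible effect of the device. Under the first reading, a non-serious reaction could be possibly related, and entered, in Group 1, yet be put down to TAVR and left out in Group 2. It is not named among the outcomes in Sections 4.2 or 7.1 that would otherwise capture it.

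**Step 3: what this does to the endpoints.** For each arm, write

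related AEs = all AEs × share judged related.

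The Section 7.2 count is the left-hand side. It is the same whether or not unrelated events are also entered, so the recording rule does not change it. But when only the left-hand side is recorded for non-serious events, the two factors on the right cannot be separated. A difference between arms could come from either factor, and equal counts could hide offsetting differences.

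**Step 4: size.** The documents give no AE rate and no attribution rate for either arm, so neither factor can be filled in. No size or direction follows.

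**The case against.** The strongest reply is that the recording rule matches the endpoints. Section 7.2 counts related events, and an event judged unrelated would not enter those counts even if it were recorded. Differential attribution comes from unmasked judgment and would remain in the related counts under full recording. This stands: a reader might infer that the filter biases the Section 7.2 counts, and it does not. What full recording adds is a comparison that needs no attribution, and the means to check attribution.

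A reader might also infer that the five-level scale contradicts the recording rule. It does not. Attribution has to precede a rule based on it, and the two lower levels are needed to classify SAEs, which are recorded whatever their relationship. Similarly, following patients for any adverse event describes surveillance, not CRF entry.

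An arm-neutral reading of *study procedure* has real support in Sections 3.4.1, 3.4.2 and 11.2, and the single reference to the intervention may be a drafting slip. That stands as a plausible reading, but none of those sections states it.

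The co-morbidity clause can be read as a specific exception to a general rule, and it leaves procedure-related worsening as an SAE. That is fair. It still conflicts with the statement that all SAEs are documented, it rests on the same judgment of relatedness, and it does not say where the excluded events go.

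Finally, Section 4.2 lists adverse event monitoring, mortality, discharge summaries and follow-up notes with no relatedness limit, and Section 11.4.3 keeps source documents for at least 6 years. Some omitted events could therefore be traced. But Section 4.2 does not say which adverse events are entered, and retrieval from notes is a weaker substitute for prospective recording. Limiting non-serious capture to save effort is a defensible aim in a single-center pilot, though with about 100 patients the saving is small.

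**Conclusion.** The point holds as one about the completeness and checkability of the safety record, and it should be fixed. As written, the plan leaves no by-arm comparison of non-serious AEs that is free of attribution. It leaves the recording of one class of SAEs unresolved, and it rests two of three safety endpoints on unmasked judgment against a term not defined for controls.

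Its reach is limited. The efficacy outcomes listed in Sections 4.2 and 7.1 are recorded outside this filter. SAEs outside the co-morbidity exception are recorded. Section 9.2 plans no test of AE or SAE counts. A reader might infer that the trial's inferential results are compromised, or that a size can be put on the distortion. The documents support neither: no planned test is affected, and any figure would rest entirely on assumed event and attribution rates.

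The conclusion assumes that the AE recording sentence is read as restrictive, and that the absence of any described masking or independent review means there is none.

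**What to change.** - In Section 8, record all AEs and SAEs in both arms through 3 months whatever the attribution, with relationship kept as a recorded field.
- Define *study procedure* once, in terms that apply identically to both arms, and use that term at every level of the attribution scale.
- Reconcile the two SAE statements so that co-morbidity SAEs are recorded and flagged as unrelated.
- In Section 7.2, summarise all AEs and all SAEs by arm, with related events as a subset.
- Leave the criteria for reporting to the IRB unchanged; they are a separate matter from what the database holds.

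The cost is protocol wording and some extra CRF entries for about 100 patients already followed for 3 months. No new visits are needed. The change is best made before enrollment, since events not recorded at the time may be hard to recover.

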9. STATISTICAL METHODS AND DETERMINATION OF SAMPLE SIZE

9.1 Sample Size Determination

The researchers could not find an evidence-based measure of effect size from the existing literature. Therefore, this project will be considered a pilot study. The researchers believe there will at least be 10-20% reduction in complications associated with the treatment based on clinical experience. An *a priori* sample size calculation was performed using a 20% reduction, and with a two-tailed hypothesis, a power of 80%, and an equal allocation ratio to treatment arms, a total of $n = 100$ participants was generated. Therefore, the researchers plan on enrolling $n = 50$ participants in each treatment arm, totaling $n = 100$ participants. The effect size yielded from the final analysis will be used to power a future, larger trial between the two treatment arms.

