3. STUDY PLAN

3.1 Study Design

This is a prospective randomized/control trial pilot study to compare clinical outcomes of common femoral artery access in patients undergoing Transcatheter Aortic Valve Replacement (TAVR) at the University of Tennessee Medical. Specifically, we will compare patients utilizing the Shockwave model (M5) Intravascular Lithotripsy (IVL) prior to standard arterial access using the modified Seldinger technique to those utilizing the standard femoral artery access via the modified Seldinger approach without the utilization of intravascular lithotripsy in heavily calcified femoral arteries.⁷

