9.2 Statistical Methods

Descriptive and frequency statistics will be used to describe the demographic, clinical, and prognostic characteristics of the randomized sample. All inferential analyses will be performed in an "intention-to-treat" fashion. A "per-protocol" analysis will also be performed. For the primary outcome, access site complications, both bivariate (chi-square or Fisher's Exact test) and multivariate (logistic regression) analyses will be performed to compare the two groups. Unadjusted odds ratios (OR) with 95% confidence intervals (95% CI) will be generated for the chi-square analyses and adjusted odds ratios (AOR) with 95% CI will be calculated for the logistic regression analyses. Baseline demographic, clinical, and prognostic characteristics will be compared between the treatment arms using between-subjects inferential analyses after randomization to test for any significant differences. Any significant

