differences at baseline will be accounted for in the primary analysis using logistic regression. Chi-square or Fisher's Exact test will be performed to compare the treatment arms on distinguishing extravasation post-closure at the end of the procedure (yes/no), comparing the need for open vascular surgery (yes/no), utilizing a PTA/stent to help with hemostasis or local vascular complications (yes/no), bleeding/hematomas (yes/no), pain or numbness in the distal extremity (yes/no), mortality related to complications associated with the vascular closure site (yes/no), and conversion to general anesthesia due to additional procedures required to address CFA access site complications (yes/no). Cross-tabulation tables with frequencies, percentages, and associated OR with 95% CI will be reported and interpreted for all bivariate analyses of categorical, secondary outcomes. For count variables and non-normal continuous parameters (number of perclose devices, LOS, and serum creatinine), Mann-Whitney U tests will be performed to compare the two treatment arms. Medians and interquartile ranges will be reported and interpreted for the non-parametric analyses of the count and continuous parameters. Survival analysis will be performed using Kaplan-Meier in order to compare the two treatment arms on "time-to-event" outcomes. Mean and median times to events will be presented. Log-rank, Breslow, and Tarone-Ware tests will be used to compare the respective groups. Survival plots will also be graphed. All analyses will be performed using SPSS Version 29 (Armonk, NY: IBM Corp.) and statistical significance will be assumed at an alpha value of 0.05.

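### Section 9.1 sizes the next trial on this pilot's observed effect, which 50 patients per arm estimate too imprecisely; the 80% power behind n = 100 also lacks a control rate, a scale and a test

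*Combined protocol and SAP*

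**What the plan says.** Section 3.1 presents the study as a pilot: "This is a prospective randomized/control trial pilot study". Section 3.3 sets the size: "We plan to enroll up to a total of 100 patients, 50 patients in each group".

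Section 9.1 explains that the literature offered no evidence-based effect size and falls back on clinical experience: "The researchers believe there will at least be 10-20% reduction in complications associated with the treatment". It then reports that a "sample size calculation was performed using a 20% reduction", two-tailed, with 80% power and equal allocation, and that this gave 100 participants. It does not give the control-arm complication rate, whether the reduction is absolute or relative, or the test assumed. No other section gives a control rate.

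Section 9.1 closes with the intended use of the result: "The effect size yielded from the final analysis will be used to power a future, larger trial between the two treatment arms".

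Section 9.2 names chi-square or Fisher's exact test for the primary outcome, adds logistic regression, promises odds ratios with 95% confidence intervals, and says that "statistical significance will be assumed at an alpha value of 0.05".

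**The concern.** The main issue is the closing sentence of 9.1. Required sample size varies roughly with the inverse square of the difference. A pilot that overstates the effect therefore produces a next trial that is much too small, and one that understates it produces a trial that is much too large. The plan ties the next trial to the observed effect and does not mention a confidence limit, a shrunken estimate or a minimum important difference. Since feeding a larger trial is the pilot's stated purpose, this is the sentence with the most practical consequence.

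The second issue is the 80%. For a binary outcome, power for a given reduction is undefined until the control rate and the scale are known. The primary outcome will be tested at 0.05, so a reader of a non-significant result needs to know the conditions under which the trial had 80% power.

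**Working it through.** **Inputs from the documents.** 50 per arm (3.3, 9.1); two-sided, 80% power, 1:1, 20% reduction, believed range 10-20% (9.1); alpha 0.05, chi-square or Fisher (9.2). **Assumed:** every control rate, because the documents give none; reductions are read as absolute unless stated. Section 3.3 says up to 100 patients; all figures take the full 50 per arm.

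**1. Reproducing n = 100.** Pooled formula, per arm, with p̄ the mean of the two rates:

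n = [1.960·√(2p̄(1−p̄)) + 0.842·√(p1(1−p1) + p2(1−p2))]² / (p1−p2)²

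- 25 vs 5%: (1.960·√0.255 + 0.842·√0.235)² / 0.04 = (0.990 + 0.408)² / 0.04 = 48.8, so 49 per arm and 98 in total.
- 22 vs 2% with continuity correction: 49.7, so 50 per arm and 100 in total.
- 30 vs 10%: 61.6, so 62 per arm.

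The stated size can therefore be matched, but only by supplying a control rate and an absolute scale.

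**2. Precision at 50 per arm.** Half-width = 1.96·√[(p1(1−p1) + p2(1−p2))/50].

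- 25 vs 15%: 1.96·√(0.315/50) = 15.6 points
- 20 vs 10%: 13.9 points
- 15 vs 5%: 11.6 points

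Each is wider than the 10-point effect being estimated.

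**3. Following the closing sentence of 9.1.** All 51 × 51 possible pilot results were enumerated with their binomial probabilities. Where the control arm had more complications, the next trial was sized for 80% power by the formula above on the two observed rates. Its true power was then evaluated at the assumed true rates. This takes *effect size* to mean the point estimate.

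One example, with truth 25 vs 15% (250 per arm needed): a pilot observing 13/50 vs 5/50 (26 vs 10%) gives n = (1.960·√0.2952 + 0.842·√0.2824)² / 0.0256 = 89.3, so 90 per arm. True power is Φ[(0.10·√90 − 1.960·√0.32)/√0.315] = Φ(−0.29), about 39%.

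Over all pilots (every share has all pilots as its denominator):

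| Assumed truth | Needed per arm | No benefit observed | True power < 50% | More than double the need |
|---|---|---|---|---|
| 25 vs 15% | 250 | 12.8% | 28.9% | 22% |
| 20 vs 10% | 199 | 10.0% | 27.9% | 23% |
| 15 vs 5% | 141 | 6.0% | 23.0% | 24% |
| 30 vs 10% | 62 | 0.7% | 12.6% | 20% |
| 25 vs 5% | 49 | 0.2% | 7.9% | 16% |

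Section 9.1 calls the next trial *larger*. At 50 per arm the formula already gives 71% power at 30 vs 10% and 81% at 25 vs 5%. If the next trial must exceed 50 per arm, the 12.6% and 7.9% both become zero. The 10-point rows do not change: at 25 vs 15%, any size up to 122 per arm has true power under 50%.

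**4. Sizing instead on a 10-point minimum important difference and the pilot's control rate.** With the same three 10-point truths, true power is under 50% in 0-3% of pilots. This comparison favours the alternative, because the chosen difference equals the true one.

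**5. When the 80% holds in this trial.** Exact power at 50 per arm for 20 absolute points, by full enumeration:

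| Rates | Chi-square | Fisher |
|---|---|---|
| 22 vs 2% | 93% | 85% |
| 25 vs 5% | 85% | 75% |
| 27 vs 7% | 80% | 70% |
| 30 vs 10% | 73% | 64% |
| 40 vs 20% | 60% | 52% |

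The highest control rate with at least 80% is 27.1% for chi-square and 23.3% for Fisher. Power passes 80% again only at control rates of about 93% (chi-square) or 97% (Fisher) and above, which are set aside as implausible. If the 20% is relative, chi-square power is about 6-10% at control rates of 10-30%.

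**The case against.** *It is only a pilot, and the next trial will have its own protocol.* This is fair as to n = 100, which can stand. But 9.1 commits in advance to how the pilot's result will be used, and that use is the pilot's purpose.

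*The sentence does not say that the point estimate alone will be used, and 9.2 promises confidence intervals.* Partly right. The shares in the working rest on the point-estimate reading, and the intervals will show the imprecision. Nothing says they will enter the sizing.

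*The control rates are invented.* They are assumptions, and they have to be, because the plan gives none. This limits how much assumed-rate material belongs in the protocol: one conditional sentence is enough.

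*The 80% is already qualified.* It is tied to a 20% reduction and to clinical experience. What is missing is narrower: control rate, scale and test.

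*The alternative also leans on a control rate from 50 patients.* This stands. If the true rate is 25%, the central 95% of observed rates is 14-38%, and a 10-point difference then needs from about 127 to 346 per arm.

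A reader might also draw three stronger conclusions that the documents do not support:

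- That n = 100 is miscalculated. It is attainable at about 25 vs 5%.
- That the sizing rule underpowers the next trial across the whole believed range. At 20-point truths this depends on a next trial no larger than the pilot, which the wording of 9.1 excludes.
- That a pilot showing no benefit is a harm of the rule. Such a result informs whether to proceed, and the plan does not say a next trial must follow regardless.

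**Conclusion.** The concern holds for the lower end of the investigators' range, read as absolute. With a true 10-point drop from assumed control rates of 15-25%, sizing on the observed point estimate leaves the next trial with under 50% true power in 23-29% of pilots and more than doubles the needed size in 22-24%. At 20-point truths the underpowering disappears once the next trial exceeds 50 per arm; some oversizing remains (16-20%).

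The missing inputs to the 80% are a secondary reporting gap. They matter because the claim fails above a control rate of about 27% (chi-square) or 23% (Fisher), and fails at any plausible control rate if the 20% is relative.

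The arithmetic is firm. The size of the problem depends on the assumed rates and on the point-estimate reading. Severity: minor to should-fix.

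**What to change.** Keep n = 100.

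1. Replace the closing sentence of 9.1 with:

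> The future trial will be powered on a pre-stated minimum important difference, using the control complication rate observed in this pilot with its 95% CI and sample sizes shown across that interval; the observed effect size and its 95% CI will be used as a check and to decide whether to proceed, not as the sole sizing input.

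2. State the control rate, the scale and the test behind n = 100. Add one sentence saying that the 80% is conditional on them and falls at higher control rates, for example to 73% (chi-square) or 64% (Fisher) at 30 vs 10%. If the 20% was meant as relative, withdraw the 80%.

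**Cost.** Protocol wording only, with no extra patients here, and a less favourable power statement. The next trial may be larger than needed if the true effect exceeds the chosen difference: a 10-point difference at a 25% control rate needs 250 per arm, against 49 if the truth is 25 vs 5%. It is also not designed to detect effects smaller than that difference. Its size still depends on a control rate from 50 patients. If the true rate is 15%, about 11% of pilots will observe under 10% (four or fewer events in 50). A 10-point absolute difference cannot then be sized, so another difference or an outside control rate would be needed.
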